7.2 PARTICIPANT DISCONTINUATION/WITHDRAWAL FROM THE STUDY

This is a pilot study involving one-time collection of data during a routine care endoscopy. Participants are free to withdraw from participation in the study at any time upon request.

An investigator may discontinue or withdraw a participant from the study if the participant is deemed ineligible based on findings from the endoscopy, or other reason.

The reason for participant discontinuation or withdrawal from the study will be recorded on the Case Report Form (CRF). Subjects who sign the informed consent form and are withdrawn may be replaced.

Withdrawn or terminated subjects will be excluded from the study. If data were collected, then they will not be used.

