7.3 LOST TO FOLLOW-UP

This pilot study involves a one-time visit with data collection. However, if for some reason a subject needs to be contacted for follow-up, then a participant will be considered lost to follow-up if he or she fails to return for a scheduled visit and is unable to be contacted by the study site staff.

The following actions must be taken if a participant fails to return to the clinic for a required study visit:

- The site will attempt to contact the participant and reschedule the missed visit and counsel the participant on the importance of maintaining the assigned visit schedule and ascertain if the participant wishes to and/or should continue in the study.
- Before a participant is deemed lost to follow-up, the investigator or designee will make every effort to regain contact with the participant (where possible, 3 telephone calls and, if necessary, a certified letter to the participant's last known mailing address or local equivalent methods). These contact attempts should be documented in the participant's medical record or study file.
- Should the participant continue to be unreachable, he or she will be considered to have withdrawn from the study with a primary reason of lost to follow-up.

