8.1.2.3 RESEARCH BIOPSY COLLECTION AND ANALYSIS

For participants enrolled in cohort B, research biopsies will be obtained from the location of device imaging. Research biopsies are taken only if the additional biopsies do not significantly increase the patient's risk or interfere with routine care procedures. The research biopsy protocol may be modified by the physician performing the procedure if necessary. During the procedure up to 10 research biopsies may be taken for use in this study. The total number of research biopsies may vary based on presence/absence of nodularity but will not exceed 10 research-specific biopsies. This number of esophageal biopsies is within the standard of care for biopsying the esophagus. Biopsies will be immediately placed in formalin for processing and histopathological analysis by [name].

Variations to the biopsy protocol (location and number of specimens obtained) are allowable and are not considered protocol deviations.

8.1.3 7 DAY FOLLOW-UP

Enrolled subjects will be contacted 7 days (+/-3 days) after administration of the device via phone or other IRB approved method. Subjects who do not meet the definition of enrolled will not be contacted. During the 7 day follow-up, the following procedures will be performed:

- 1) Assess for adverse events
- 2) Complete eCRF and data entry

No additional follow-up is anticipated.

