
9.3 POPULATIONS FOR ANALYSES

All subjects who were administered the probe, regardless of enrolling cohort, will have data included for optimization unless withdrawn per section 7.2. For this study, an enrolled subject is defined as a subject who was successfully administered the device and for whom we have evaluable data.

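### Sections 7.2, 7.3 and 9.3 together discard complete imaging data when only the day-7 safety contact is missed, and 7.2 separately leaves post-imaging withdrawal and replacement open-ended

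*Combined protocol and SAP*

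**What the plan says.** Section 7.2 excludes anyone withdrawn or terminated and adds: "If data were collected, then they will not be used". It lets the investigator withdraw a participant "if the participant is deemed ineligible based on findings from the endoscopy, or other reason", requires the reason to be recorded on the CRF, and permits replacement.

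Section 7.3 says that a subject who remains out of reach is lost to follow-up: "he or she will be considered to have withdrawn from the study with a primary reason of lost to follow-up". Before that, the site must make every effort at contact ("where possible, 3 telephone calls and, if necessary, a certified letter").

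Section 9.3 defines the analysis population as everyone given the probe, whose data "will have data included for optimization unless withdrawn per section 7.2".

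The only scheduled follow-up is in 8.1.3: "Enrolled subjects will be contacted 7 days (+/-3 days) after administration of the device via phone or other IRB approved method". Its content is safety ("Assess for adverse events") and completion of the eCRF. Sections 8.1.2 and 9.3 count a subject as enrolled once the device has been used and the data are evaluable; the day-7 contact is not part of that definition.

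**The concern.** Two separate mechanisms are at work.

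The first is avoidable data loss. Everything that bears on the two objectives (tissue contact, and squamous versus Barrett's classification) is gathered at the endoscopy or from its biopsies. The day-7 contact adds nothing on accuracy, yet missing it can remove the subject's whole record. In Cohort B that may include up to 10 research biopsies taken for the study and then left unused.

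The second is selection. Withdrawal after imaging is allowed for any reason, with replacement. Section 6.1 says part of the optical data is displayed live, and 10.1.6 says the clinical study PI performs the endoscopies. No text requires the withdrawal decision to be made without reference to the device output. If subjects with poor contact or a wrong classification were more likely to be withdrawn, both the adequacy result and the sensitivity estimate would look better than the device deserves.

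**Working it through.** **1. The chain for a missed day-7 contact.** Under 7.3, persistently unreachable means withdrawn. Under 7.2, withdrawn means that collected data are not used. Under 9.3, subjects withdrawn under 7.2 are left out. Section 8.1.3 calls only enrolled subjects, who by definition have evaluable data. So every subject removed by this route already has usable images.

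**2. Size of the loss.** Section 9.2 gives 42 + 40 = 82 subjects with no dropout allowance. The documents give no rate for unreachable subjects, so I assume 5–15%: 0.05 × 82 = 4.1 and 0.15 × 82 = 12.3, or about 4–12 image sets. If the discard rule stayed, reaching 14 evaluable per Cohort A group would need 14/0.95, 14/0.90 or 14/0.85, that is 15, 16 or 17 imaged per group at 5%, 10% or 15% loss.

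**3. The plan's own figure.** Section 9.2 states 85% power with 14 evaluable patients per group, for sensitivity 95% against 70%. It gives no alpha and no cut-off. An exact binomial rule of at least 13 of 14 reproduces it, with P(X ≥ 13) = 14p¹³(1 − p) + p¹⁴:
- p = 0.95: 0.847 (power)
- p = 0.70: 0.0475 (one-sided alpha)

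The 13/14 criterion and a one-sided 0.05 level are therefore inferred from the match.

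**4. Effect of losing one subject of 14, not replaced.** At exact alpha ≤ 0.05 the rule becomes 13 of 13, with power 0.95¹³ = 51.3%. Much of that drop comes from the discreteness of the cut-off: at least 12 of 13 gives 86.5% power but alpha 0.064. For estimation, which is what 9.1 plans, the effect is smaller: the exact 95% lower limit is 66.1% for 13/14 and 64.0% for 12/13.

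**5. Illustration of selection after imaging.** Let S be true patient-level sensitivity and f the share of misclassified patients withdrawn and replaced. Expected observed sensitivity is S / [S + (1 − S)(1 − f)]. The values of f are assumptions. At S = 0.70, the lowest acceptable value in 9.2:

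| f | Observed sensitivity | P(at least 13/14) |
|---|---|---|
| 0 | 70.0% | 4.7% |
| 0.25 | 0.70/0.925 = 75.7% | 11.1% |
| 0.50 | 0.70/0.85 = 82.4% | 26.4% |

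On a single data set, 12/14 (85.7%) becomes 12/13 (92.3%) if one misclassified patient is removed, and 13/14 (92.9%) if that patient is replaced by one correctly classified.

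**The case against.** The strongest objection is that the day-7 step is an inference. Section 7.3 speaks of failing to return to the clinic, describes the study as a single visit, and treats later contact as exceptional, whereas 8.1.3 is a phone contact for every enrolled subject. This stands as a reason for moderate rather than high confidence. It does not remove the point, because no text exempts the day-7 call and the sections are unreconciled on any reading.

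Four stronger readings are tempting, and the documents do not support them:
- *One unanswered call means withdrawal.* Section 7.3 applies only after repeated attempts.
- *Missed calls bias sensitivity.* They would do so only if being reachable were related to image accuracy, and nothing suggests that.
- *Adverse events in withdrawn subjects are lost.* Section 8.2.5 requires all events on study to be documented, and 10.1.6 has an independent monitor review them. The conflict with 7.2 is about whether they are used in the tables.
- *The plan tests against 13 of 14.* Section 9.1 rules out hypothesis tests, and 9.4 computes sensitivity by site, not by patient.

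On selection, 8.1.2.1 bars the use of device images to diagnose or categorize participants, the withdrawal reason is recorded, and exclusion for ineligibility seen at endoscopy is legitimate. All of that stands. But the bar concerns categorization, not withdrawal, and recording a reason does not limit it.

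Replacement can restore the sample size, but it is optional, exposes another patient to the procedure, and does not undo selection. Pooling the two Barrett's groups (28 patients, at least 24 correct: power 98.8%, alpha 0.0474) would make a few losses matter less.

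**Conclusion.** The point holds in two parts. First, as written, the rules discard complete and evaluable data for a missed safety contact. The cost is precision: about 4–12 of 82 image sets under an assumed 5–15% loss. Confidence in this part is moderate because of the clinic-visit wording in 7.3.

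Second, open-ended withdrawal with replacement after imaging leaves a route to selection bias in sensitivity and in the tissue-contact objective. The documents give no sign that it would be used that way. The 76–82% reading, and the rise from 4.7% to 11–26%, rest on an assumed withdrawal pattern, a patient-level model and an inferred criterion; they show scale and are not a forecast. The change should be made: it is cheap, and discarding these data brings no scientific benefit.

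**What to change.** 1. **Section 7.3.** State: *A subject not reached at day 7 is missing the safety follow-up only; imaging, pathology and adverse-event data to last contact are kept and analysed.* Align the section with the phone contact in 8.1.3.
2. **Section 7.2.** Replace the last sentence with: *Data collected before withdrawal are kept and analysed unless the participant asks for removal.* This is subject to the consent wording, which is not in the documents reviewed. After probe use, limit investigator exclusion from the accuracy analysis to ineligibility on endoscopy, pathology or history, decided without reference to the device images. Keep every subject given the probe in the adequacy and safety tables. Report each withdrawn or replaced subject with the reason, and add a supporting accuracy analysis that includes them.
3. **Section 9.3.** Change the withdrawal exception to match the new 7.2, and reconcile 7.2 with 8.2.5 so that recorded adverse events are still tabulated.

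The cost is a short amendment to these sections, plus a check of the consent form. No extra subjects are needed. The downside is that a few imperfect cases stay in the tables.

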7.3 LOST TO FOLLOW-UP

This pilot study involves a one-time visit with data collection. However, if for some reason a subject needs to be contacted for follow-up, then a participant will be considered lost to follow-up if he or she fails to return for a scheduled visit and is unable to be contacted by the study site staff.

The following actions must be taken if a participant fails to return to the clinic for a required study visit:

- The site will attempt to contact the participant and reschedule the missed visit and counsel the participant on the importance of maintaining the assigned visit schedule and ascertain if the participant wishes to and/or should continue in the study.
- Before a participant is deemed lost to follow-up, the investigator or designee will make every effort to regain contact with the participant (where possible, 3 telephone calls and, if necessary, a certified letter to the participant's last known mailing address or local equivalent methods). These contact attempts should be documented in the participant's medical record or study file.
- Should the participant continue to be unreachable, he or she will be considered to have withdrawn from the study with a primary reason of lost to follow-up.

8 STUDY ASSESSMENTS AND PROCEDURES

8.1 SCHEDULE OF ACTIVITIES (SOA)

Procedures	Screening ¹	Enrollment ¹	Post-EGD	7 Day Follow-Up (+/-3 days)
Informed consent	X			
Eligibility Assessment	X	X		
Demographics	X			
Medical history	X			
Urine Pregnancy Test		X ²		
Routine Care EGD		X ³		
Esophageal Images		X		
Research biopsies		X ⁶		
Administer Probe ⁵		X		
Collection of Pathology Results			X ⁴	
Adverse event review and evaluation	X	X		X
Complete Case Report Forms (CRFs)	X	X	X	X

¹Screening and enrollment can occur on the same day

²Urine pregnancy tests will be performed on females with reproductive potential.

³EGD is performed as part of routine care. Subjects would be receiving this EGD regardless of participation in the study.

⁴Only if biopsies are taken for routine clinical care during the procedure. If biopsies are taken for routine clinical care during this procedure, then pathology results will be collected as part of this study, and slides may be requested from clinical biopsies for use in this study after they have yielded their results for routine care.

⁵ Probe utilized can be either the OCT probe (Cohort A) or the combined a/LCI-OCT probe (Cohort B), based on Investigator discretion at time of enrollment.

⁶ Research biopsies may be taken for participants in Cohort B.

8.1.1 SCREENING

The following procedures will be performed during the screening visit:

- 1) Identification of potential subjects via IRB approved methods
- 2) Informed consent (see section 10.1.1 for details regarding the informed consent process)
- 3) Collection of data including demographics and medical history
- 4) Complete CRFs and data entry

8.1.2 ENROLLMENT

The following procedures will be performed during the enrollment visit:

- 1) Re-assess eligibility

- 2) Completion of urine pregnancy test on women with reproductive potential
- 3) Administration of OCT-probe for Cohort A or combined a/LCI-OCT probe for Cohort B and completion of esophageal images during routine care upper endoscopy
- 4) Collection of data from endoscopy
- 5) Collection of co-localized research biopsies (Cohort B)
- 6) Adverse event assessment
- 7) Complete CRFs and data entry

For this study, an enrolled subject is defined as a subject who was successfully administered the OCT device and for whom we have evaluable data.

***Screening and enrollment can occur on the same day.

8.1.2.1 PROBE ADMINISTRATION, ESOPHAGEAL IMAGES, AND RESEARCH BIOPSIES

Subjects will proceed with routine care EGD, during which esophageal landmarks will be identified, and the OCT or a/LCI-OCT device administered. In brief, the probe will be affixed to the end of the endoscopy using a plastic band, in a manner similar to that used to deliver other devices into the esophagus. The device and endoscope tip will be passed through the posterior pharynx and the upper esophageal sphincter under direct endoscopic visualization. Areas of normal squamous epithelium can be easily identified endoscopically, as can areas of columnar mucosa in the esophagus, based on the endoscopic appearance. The OCT or a/LCI-OCT combined device will be apposed to both normal and columnar (Barrett's) tissue, by deflection of the endoscope tip. Images will be acquired by the device, as detailed below, and subjects enrolled in cohort B will also receive research-specific biopsies as detailed below. The indentation on the tip of the probe will create a transient tissue bump that is visible endoscopically to allow for concurrent research biopsies after images are taken. After acquisition of these images and research biopsies (as applicable), the remainder of the study will be performed as per the standard of care.

Erosions, erosive disease, and areas of inflammation will be avoided when placing the paddle for probe administration. Adequacy of device-to-epithelium contact will be measured based on the quality of the OCT image. In images with poor contact, esophageal mucosal layers are poorly defined. In this situation, the probe will be repositioned in an effort to improve image quality. A good image is that in which esophageal mucosal layers are clearly defined in the OCT image.

COHORT A:

During the procedure, the OCT device will be administered, and at least one white light image and at least one narrow band image will be taken from the following locations of the esophagus:

- 1) 3 centimeters above the top of the gastric folds (TGF-3)
- 2) 5 centimeters above the top of the gastric folds (TGF-5)
- 3) Any planned clinical biopsy locations

COHORT B:

During the procedure, the a/LCI-OCT device will be administered, and at least one white light image and at least one narrow band image will be taken from the following locations of the esophagus:

- 1) 3 centimeters above the top of the gastric folds (TGF-3)
- 2) 5 centimeters above the top of the gastric folds (TGF-5)

- 3) Co-localized research-specific biopsies will be taken at the imaging location
- 4) Any planned clinical biopsy locations

Variations to the imaging protocol (location and number of images obtained) are allowable and are not considered protocol deviations.

Device images will not be used to diagnose or categorize participants. Participants will be categorized based on endoscopy, clinical pathology and medical history, as per usual clinical practice. If no biopsies are taken for clinical care, and the subject is presenting for upper endoscopy for GI conditions without esophageal symptomatology, then the epithelium will be assumed to be normal squamous epithelium per the endoscopic imaging.

8.1.2.2 PATHOLOGY REPORTS AND SLIDES ACQUISITION

If clinical biopsies are obtained during the enrollment upper endoscopy, then results from those clinical biopsies will be obtained for this research study after they have yielded their results for routine care.

Slides may be requested from clinical biopsies and used as part of this research study.

8.1.2.3 RESEARCH BIOPSY COLLECTION AND ANALYSIS

For participants enrolled in cohort B, research biopsies will be obtained from the location of device imaging. Research biopsies are taken only if the additional biopsies do not significantly increase the patient's risk or interfere with routine care procedures. The research biopsy protocol may be modified by the physician performing the procedure if necessary. During the procedure up to 10 research biopsies may be taken for use in this study. The total number of research biopsies may vary based on presence/absence of nodularity but will not exceed 10 research-specific biopsies. This number of esophageal biopsies is within the standard of care for biopsying the esophagus. Biopsies will be immediately placed in formalin for processing and histopathological analysis by [name].

Variations to the biopsy protocol (location and number of specimens obtained) are allowable and are not considered protocol deviations.

8.1.3 7 DAY FOLLOW-UP

Enrolled subjects will be contacted 7 days (+/-3 days) after administration of the device via phone or other IRB approved method. Subjects who do not meet the definition of enrolled will not be contacted. During the 7 day follow-up, the following procedures will be performed:

- 1) Assess for adverse events
- 2) Complete eCRF and data entry

No additional follow-up is anticipated.

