history of or current dysplastic Barrett's Esophagus (High Grade Dysplasia (HGD) or Low Grade Dysplasia (LGD)). Cohort B will consist of 20 patients in each of the two groups; current dysplastic Barrett's Esophagus of either High Grade Dysplasia (HGD) or Low Grade Dysplasia (LGD)) and normal controls (with or without history of previous successful esophageal ablation). Classification of patients will occur based on medical history and clinical pathology obtained during the EGD.

Description of Sites/Facilities
Enrolling Participants:

UNC Chapel Hill (Enrolling Site)
Duke University (Device Manufacture)

Description of Study Intervention:

The purpose of this instrument is to obtain optical measurements from the esophageal mucosa via an endoscopic probe. The modalities used by this probe are angle-resolved low-coherence interferometry (a/LCI) and Optical Coherence Tomography (OCT); depth-resolved optical imaging technology. These optical readings provide indications of subsurface tissue architecture and will assist in the detection and diagnosis of metaplastic and dysplastic conditions such as Barrett's esophagus.

The probe is designed to be used in conjunction with the visual guidance provided by a commercial endoscope. The probe has mechanical features similar to a radiofrequency ablation (RFA) "paddle", which is externally attached to an endoscope to provide ablative therapy under visual guidance of the endoscope.

[figure not shown]
Once inserted into a patient's esophagus and placed against the tissue surface, the probe will acquire 2D OCT images of the tissue surface at operator-selected locations. Some of the optical data received will be displayed in real-time. All optical data will also be stored on a computer for post hoc analysis.

During Phase I the OCT instrument will be used alone. The components of the OCT device are grouped into the following modules: 1) Optical probe, 2) OCT engine, 3) computer system and 4) physical enclosure. Phase II of the study will consist of a dual modality a/LCI - OCT combined probe. The combined probe will consist of the following modules: 1) Optical probe, 2) OCT engine, 3) a/LCI engine, 4) computer system and 4) physical enclosure. See section 6.1 for detailed device descriptions.

Study Duration: 24 Months

Participant Duration: 7 days

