1.2 SCHEMA

1.3 SCHEDULE OF ACTIVITIES (SOA)

Procedures ⁷	Screening ¹	Enrollment ¹	Post-EGD	7 Day Follow-Up (+/-3 days)
Informed consent	X			
Eligibility Assessment	X	X		
Demographics	X			
Medical history	X			
Urine Pregnancy Test		X ²		
Routine Care EGD		X ³		
Esophageal Images		X		
Research Biopsies		X ⁶		
Administer Probe		X ⁵		
Collection of Pathology Results			X ⁴	
Adverse event review and evaluation	X	X		X
Complete Case Report Forms (CRFs)	X	X	X	X

¹Screening and enrollment can occur on the same day

²Urine pregnancy tests will be performed on females with reproductive potential.

³EGD is performed as part of routine care. Subjects would be receiving this EGD regardless of participation in the study.

⁴Only if biopsies are taken for routine clinical care during the procedure. If biopsies are taken for routine clinical care during this procedure, then pathology results will be collected as part of this study, and slides may be requested from clinical biopsies for use in this study after they have yielded their results for routine care.

⁵Probe utilized can be either the OCT probe (Cohort A) or the combined a/LCI-OCT probe (Cohort B), based on Investigator discretion at time of enrollment.

⁶ Research biopsies may be taken for participants in Cohort B, per discretion of principal investigator.

⁷ Both cohorts (A and B) will follow the same schedule of activities, unless specifically mentioned otherwise.

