4.3 END OF STUDY DEFINITION

A participant is considered to have completed the study if he or she has completed all phases of the study including the last visit or the last scheduled procedure shown in the Schedule of Activities (SoA), Section 1.3.

The end of the study is defined as completion of the last visit or procedure shown in the SoA in the trial.

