8.2.5 TIME PERIOD AND FREQUENCY FOR EVENT ASSESSMENT AND FOLLOW-UP

The occurrence of an adverse event (AE) or serious adverse event (SAE) may come to the attention of study personnel during study visits and interviews of a study participant presenting for medical care, or upon review by a study monitor.

All AEs will be captured on the appropriate case report form (CRF). Information to be collected includes event description, time of onset, clinician's assessment of severity, relationship to study device (assessed only by those with the training and authority to make a diagnosis), and time of resolution/stabilization of the event. All AEs occurring while on study must be documented appropriately regardless of relationship. All AEs will be followed to adequate resolution.

Any medical condition that is present at the time that the participant is screened will be considered as baseline and not reported as an AE. However, if the study participant's condition deteriorates at any time during the study, it will be recorded as an AE.

Changes in the severity of an AE will be documented to allow an assessment of the duration of the event at each level of severity to be performed. AEs characterized as intermittent require documentation of onset and duration of each episode.

Research staff will record all adverse events with start dates occurring any time after informed consent is obtained until completion of study participation. At each study visit, the investigator will inquire about the occurrence of AE/SAEs since the last visit. Events will be followed for outcome information until resolution or stabilization.

All new or worsening adverse events (AEs) will be collected for all subjects from the time of subject enrollment through completion or termination of the clinical investigation. This includes AEs that are not device or procedure related.

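### The only post-procedure adverse event contact may fall on day 4 of a stated 7-day participation, and Section 8.2.5 gives two different end-points for adverse event collection

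*Combined protocol and SAP*

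**What the plan says.** The synopsis (Section 1.1) states "Participant Duration: 7 days". Section 8.1.3 sets the follow-up: "Enrolled subjects will be contacted 7 days (+/-3 days) after administration of the device via phone or other IRB approved method". Both Schedule of Activities tables (Sections 1.3 and 8.1) carry the same tolerance in the column header. Section 8.1.3 adds "No additional follow-up is anticipated".

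Section 4.3 ties completion to the schedule and not to a calendar day: a participant is complete on having "completed all phases of the study including the last visit or the last scheduled procedure shown in the Schedule of Activities". The follow-up contact is the last column of that schedule.

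Section 8.2.5 describes AE collection in two ways. One sentence reads "Research staff will record all adverse events with start dates occurring any time after informed consent is obtained until completion of study participation". A later paragraph in the same section has new or worsening AEs collected from enrollment until the investigation as a whole is completed or terminated. The section also allows for events learned of when a participant presents for care or when a monitor reviews records, requires the time of onset to be recorded, and has known events followed to resolution or stabilization.

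**The concern.** A call can record only what has already happened, so the two halves of the tolerance are not equivalent. Because onset time is collected, a day-10 call can be cut back to a day 0-7 window at analysis. A day-4 call cannot be extended to day 7, because nobody asks again.

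Read with Section 4.3 and the first of the two sentences in Section 8.2.5, a day-4 call also completes the subject's participation. The second statement in Section 8.2.5 points to a much later close. The plan therefore does not settle how long each subject is under AE observation, or whether an event starting on day 6 in a subject called on day 4 belongs in the data.

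What is at stake is complete safety ascertainment for a newly developed device. Sections 2.3.1 and 2.3.3 name infection, aspiration, bleeding and perforation among the risks, and Section 8.1.2.3 allows up to 10 research biopsies per Cohort B subject.

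**Working it through.** **Inputs from the documents.** Nominal contact day 7 and tolerance 3 days (Sections 8.1.3, 1.3 and 8.1); stated participation 7 days (Section 1.1); bleeding risk from biopsy below 1/1,000 (Section 2.3.3); 40 subjects in Cohort B (Section 9.2). There is no AE rate or power figure on this point to reproduce.

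**Window.**
- Earliest call: 7 − 3 = day 4. Latest call: 7 + 3 = day 10.
- Days of the stated participation not covered by a day-4 call: 7 − 4 = 3, and 3/7 = 43%.
- Longest to shortest permitted observation, counted from device administration: 10/4 = 2.5. This compares two permitted extremes and is not typical variation.

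**Share of day 0-7 onsets that start after a day-4 call.** The documents give no onset times, so the distribution F is an assumption. The share is 1 − F(4)/F(7). For an exponential onset with mean m days it equals (e^(−4/m) − e^(−7/m)) / (1 − e^(−7/m)).

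| Assumed onset | Share after day 4 |
|---|---|
| Exponential, mean 0.5 day | 0.03% |
| Exponential, mean 1 day | 1.7% |
| Exponential, mean 2 days | (0.1353 − 0.0302)/0.9698 = 10.8% |
| Exponential, mean 3 days | 18% |
| Exponential, mean 7 days | 31% |
| Uniform over 7 days | 3/7 = 43% |

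**Average over subjects.** This assumes that calls are spread evenly over the seven permitted days, 4 to 10. Calls on days 7 to 10 lose none of the day 0-7 onsets.
- Uniform onset: (3/7 + 2/7 + 1/7)/7 = 6/49 = 12%.
- Exponential, mean 2 days: losses of 10.8%, 5.3% and 2.0% for calls on days 4, 5 and 6, so (10.8 + 5.3 + 2.0)/7 = 2.6%.

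**Scale of one named risk.** At the stated upper bound, expected biopsy bleeds in Cohort B are at most 40 × 0.001 = 0.04 if each subject is counted once. The point therefore rests on AE ascertainment in general and not on bleeding.

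**With the contact on days 7 to 10.** The ratio of longest to shortest observation falls to 10/7 = 1.43, and no part of the stated 7 days is left without enquiry in a contacted subject.

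**The case against.** The strongest reply is that a symmetric tolerance around a nominal 7-day call is ordinary practice, and that Section 8.2.5 does not clearly close AE collection on day 4. Its second statement extends collection to the end of the investigation, and it names passive routes by which later events can be learned of. This stands in part. What may end on day 4 is active enquiry, so a reader who infers that later events are missed goes beyond the text: they may go unrecorded. The reply does not remove the gap. Passive routes depend on the subject presenting for care or on a record reaching a monitor, and two end-points in one section are themselves a reason to state one.

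Three stronger readings are tempting, and the documents do not support them:
- **A 7-day AE rate that is uninterpretable.** No such rate is defined. Section 9.1 lists estimates generically, Section 9.4 contains no AE analysis, and the synopsis gives no endpoints.
- **A rate biased low.** Calls on days 8 to 10 can add onsets beyond day 7 just as calls on days 4 to 6 can lose some. The net effect on a crude proportion depends on call timing and onset, and neither is known.
- **Cohort differences that reflect call timing.** Both cohorts follow the same schedule, no between-cohort AE comparison or hypothesis test is planned, and nothing suggests that calls would be timed differently.

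It can also be said that fewer calling days would push more subjects into lost to follow-up, which Section 7.3 treats as withdrawal and Section 7.2 excludes from use. Section 7.3 turns on a subject remaining unreachable after repeated attempts, not on the width of the window, and the latest permitted day would not change.

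**Conclusion.** The point holds as a modest defect in AE ascertainment. The sole scheduled post-procedure enquiry may precede the end of the stated participation by up to 3 of 7 days, no later contact is planned, and the end of AE collection is stated in two ways that do not agree.

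The size cannot be fixed from the documents. For a subject called on day 4 it runs from about 0% to 43% of day 0-7 onsets, depending wholly on the assumed onset distribution. Averaged over evenly spread calls it is about 3% (exponential, mean 2 days) to 12% (uniform). These are shares of onsets not actively asked about, and some of those events may still be captured passively. In an 82-subject pilot with no planned AE comparison the analytic effect is limited. The case for acting is that the early half of the tolerance loses information that cannot be recovered, and that removing it costs little.

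**What to change.** 1. In Section 8.1.3 and in the follow-up column header of both Schedule of Activities tables (Sections 1.3 and 8.1), set the contact to no earlier than day 7 and up to day 10 (−0/+3 days).
2. In Section 9.4, state that AEs with onset from device administration through day 7 will be tabulated as the common window for all contacted subjects, using the onset time that Section 8.2.5 already requires.
3. In Section 8.2.5, replace the two end-points with one statement that agrees with that window, and say how an event learned of passively after the contact is recorded. Make the participant duration in Section 1.1 and the completion rule in Section 4.3 consistent with it.

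The cost is four permitted calling days instead of seven, so slightly tighter scheduling. No contact, visit or staff is added, and the latest calling day stays the same.
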